1.7 Statistical Methodology

The analysis will consist of data descriptions and statistical hypothesis testing. Throughout this document, the following terminology is used for indicating the type of descriptive analysis to be performed:

- ‘Descriptive statistics’ is used to indicate the description to be provided for quantitative variables, and includes the mean, standard deviation, 95% confidence interval (CI) on the mean, minimum, 1st quartile, median, 3rd quartile, maximum,

- number of available observations, and number of missing observations.
- ‘Frequency distribution’ is used to indicate the description to be provided for categorical variables and consists of numbers and percentages for each of the scores or categories.

For the variables recorded for both AS and PsA patients the descriptions will be given for all patients as well as separately for each subgroup.

The relationship between TWPI and disease activity at baseline and between TWPI and clinical evaluations at baseline will be evaluated by means of the Spearman rank correlation coefficient.

The relationship between work status and disease activity and between work status and clinical evaluations will be evaluated by means of analysis of variance, controlled for indication, if applicable.

1.8 Patient Population

The following analysis sets are considered for the analysis:

Intention to Treat (ITT) Set: All patients enrolled in the study, who received at least one dose of adalimumab, and for whom any follow-up data are available.

Per Protocol Set (PPS): All patients of the ITT Set without any major protocol deviations. Protocol deviations will be reviewed and classified as minor or major during a data review that will be held before database lock.

Safety Set: All patients enrolled in the study, who received at least one dose of adalimumab, and for whom any follow-up data are available.

All baseline and efficacy data will be analysed on the basis of the PPS. In case the difference between the ITT Set and PPS exceeds 10% of the patients of the PPS, the TWPI data will also be analysed for the ITT Set.

The analysis of adverse events and of the course of the study will be performed on the basis of the Safety Set.

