Study termination

- Study completion or study withdrawal date.
- Reason for study termination:
 - Study completion
 - Withdrawal of consent.
 - Lost to follow-up.
 - Discontinued due to administrative reasons.
 - Death.
 - Serious adverse event.
 - Discontinued due to other reason.

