 2. If 2 or more response options are ticked, the highest score is recorded.
 3. In case of a response between 2 tick boxes, the lower score is recorded.
- Serious Adverse Events (SAEs)
 - SAEs are coded by AbbVie using the Medical Dictionary for Regulatory Activities (MedDRA). One or more Preferred Terms (PT) are associated with each SAE. These terms will be provided to DICE who will map them to the corresponding System Organ Class (SOC).
 - Study-emergent SAE: An SAE is considered study-emergent if its onset date is on or after the date of informed consent and at most 70 days after the date of last administration of adalimumab.
 - Relation of SAE with study medication:
 - o Related: Probably related, possibly related, probably not related, unknown, not reported, missing.
 - o Not related: Not related.
 - Non-Serious Adverse Events (AE)
The CRF allowed the reporting of non-serious adverse events. These events are coded using MedDRA Version 20.0.
 - AS/PsA treatments recorded at baseline and during the study are coded using the World Health Organization (WHO) Drug Dictionary, Version 1 December 2011.

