1.10 Changes from the Analysis Foreseen in the Protocol

For the DLQI the protocol only foresaw an analysis of the total score and the categories. In order to provide additional information descriptions will also be provided for the 6 scales of the DLQI, and for the regrouped categories ≤ 5 and > 5 .

The protocol foresaw to analyse the evolution of the work productivity data, the health-related quality of life scores, and the disease activity measures and clinical evaluations based upon the data collected in time windows around the foreseen study visits. Since data were collected in the CRF around the planned visits, it was decided to analyse the data by reported study visit.

Since an important proportion of patients dropped out before the Month 18 visit it was decided also to perform analyses for the last observation after baseline.

The protocol did not foresee to perform an analysis of the safety data. It was decided to perform an analysis of adverse events and of the course of the study and for this purpose a safety analysis set was defined.

In order to better comprehend the effect of employment status it was decided to provide frequencies of extra-articular disease manifestations broken down by employment status.

The protocol foresaw to primarily perform the analysis on the basis of the PPS and to perform a sensitivity analysis of the TWPI on the ITT Set. It was decided only to perform the latter analysis in case the difference between the two analysis sets exceeds 10% of the patients of the PPS.

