4. COURSE OF THE STUDY

The analysis is performed for all patients and broken down by indication.

Study duration and study termination

- Descriptive statistics for study duration.
- Frequency distribution for reason for study termination.

Adalimumab treatment

- Descriptive statistics for treatment duration.
- Frequency distribution of any change in adalimumab treatment.
- For the patients for whom any change in adalimumab treatment was recorded, list of the data recorded concerning adalimumab treatment.

Concomitant Medications

- Frequency distribution of subjects taking other AS/PsA medication by WHO-DRUG anatomical class.
- Frequency distribution of subjects taking other AS/PsA medication by WHO-DRUG anatomical and therapeutic class.

Employment Situation

- Frequency distribution of any change in employment situation.
- For the patients for whom any change in employment situation was recorded, list of the data recorded at each visit concerning employment situation.

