6. SAFETY DATA

6.1 Serious Adverse Events

- By-patient list of individual data for SAEs that are not study-emergent.
- By-patient list of individual data for study-emergent SAEs.
- Frequency distributions of patients with study-emergent SAEs¹, and with study-emergent SAEs causing treatment discontinuation.
- Frequency distributions of patients with study-emergent SAEs by MedDRA SOC.
- Frequency distributions of patients with study-emergent SAEs by MedDRA SOC and PT¹.
- Frequency distributions of patients with study-emergent SAEs by MedDRA SOC, PT, and maximal severity.
- Frequency distributions of patients with study-emergent SAEs by MedDRA SOC, PT, and strongest relationship.

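### Study termination and duration are tabulated only for treated patients with follow-up data, so patients lost early may be missing from the table meant to count them

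*SAP*

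**What the plan says.** SAP 1.8 defines the ITT Set as "Intention to Treat (ITT) Set: All patients enrolled in the study, who received at least one dose of adalimumab", followed by a condition that some follow-up data exist. The Safety Set is given as "Safety Set: All patients enrolled in the study, who received at least one dose of adalimumab, and for whom any follow-up data are available". After the set name, the two definitions are identical.

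SAP 1.8 then states: "The analysis of adverse events and of the course of the study will be performed on the basis of the Safety Set". The course of the study is SAP 4, which lists study duration, "Frequency distribution for reason for study termination", adalimumab treatment duration, concomitant medication and changes in employment. Among the termination reasons recorded (SAP 1.5) is "Lost to follow-up".

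SAP 1.10 explains that the protocol planned no safety analysis, that adverse event and course-of-study analyses were added, and that "for this purpose a safety analysis set was defined".

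Neither document says what counts as follow-up data.

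**The concern.** Having follow-up data is something that happens after dosing. Using it as an entry condition for a table of study termination selects on the outcome being described. A treated patient who never comes back is the clearest case of loss to follow-up, and may be the one patient the table cannot contain.

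The gap need not be short. Follow-up visits take place in routine practice, the first preferably at Month 3, and the protocol requires no extra visits (Protocol 6.4 and 6.5). A patient who stops at any time before that first return could have no post-baseline visit. Protocol Appendix G labels the last column as Month 18 or termination, but attendance still follows routine care.

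What is at stake is the account of attrition. SAP 1.10 acknowledges substantial dropout before Month 18 and adds last-observation analyses because of it, so readers will rely on the termination table to judge how far those analyses can be trusted.

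**Working it through.** **Plan's own figure.** The documents give no size for the Safety Set and no number of treated patients without follow-up. The plan's precision table for the change in TWPI does not enter this point.

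**Step 1: does another output show the excluded patients?**
- SAP 2.1 counts only the ITT Set and the Per Protocol Set.
- SAP 2.2 covers everyone enrolled, but only for calendar dates.
- SAP 4 says its analysis is for all patients and by indication. SAP 3 opens the same way, and the contrast there is AS and PsA combined against each separately. It does not override the assignment to the Safety Set in SAP 1.8.

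So no table shows how many treated patients fall outside the set.

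**Step 2: can those patients be tabulated from data already collected?** Yes.
- The adalimumab start date is a baseline item (SAP 1.5), so dosing can be established without a return visit.
- SAP 1.6 computes study duration as 12 × (completion or withdrawal date − inclusion date) / 365.25. SAP 1.9 replaces a missing completion or withdrawal date with the date of last contact.
- Treatment duration is 12 × (earlier of stop and completion dates − start date + 14) / 365.25. For a patient whose last contact is the start date, this gives 12 × 14 / 365.25 = 0.46 months.

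**Step 3: direction for termination and duration.** Let N be the number treated, L the number lost to follow-up, and e the number excluded.
- If all the excluded were lost, the table shows (L − e)/(N − e), which is below L/N whenever L < N. More generally, a reason is understated when it is more common among the excluded than overall.
- The mean duration over all treated is [(N − e) × mean of those kept + e × mean of those excluded]/N. It is below the mean of those kept whenever the excluded have shorter durations. In the extreme case where they contribute zero study time, the reported mean is too high by a factor N/(N − e).

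**Step 4: illustration.** Assumed inputs: N = 200 (the planned enrolment, all treated), L = 40, 10 patients with a serious adverse event (SAE), and e from 5 to 30. Only the 200 is in the documents.

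| e | Set | Lost, (40 − e)/(200 − e); all treated 20.0% | Largest inflation of mean study duration, 200/(200 − e) | SAE %, no SAE patient excluded, 10/(200 − e); all treated 5.00% | SAE %, two SAE patients excluded, 8/(200 − e) |
|---|---|---|---|---|---|
| 5 | 195 | 35/195 = 17.9% | 1.026 | 5.13% | 4.10% |
| 10 | 190 | 30/190 = 15.8% | 1.053 | 5.26% | 4.21% |
| 20 | 180 | 20/180 = 11.1% | 1.111 | 5.56% | 4.44% |
| 30 | 170 | 10/170 = 5.9% | 1.176 | 5.88% | 4.71% |

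With e = 0 every figure equals its all-treated value.

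**Step 5: adverse events.** The tables are of the form "Frequency distributions of patients with study-emergent SAEs by MedDRA SOC", with the Safety Set as denominator. SAP 1.6 states: "An SAE is considered study-emergent if its onset date is on or after the date of informed consent", with the window ending 70 days after the last administration. No return visit is needed for an event to qualify. If follow-up data means a visit, a patient with a reported early event and no visit leaves both numerator and denominator. If an event report itself counts, non-returners enter only when something was reported, so entry depends on the outcome. The table in Step 4 shows that the percentage can move either way, by less than one percentage point here.

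**The case against.** **The exclusion is not certain.** The follow-up condition is undefined. A completed termination record (SAP 1.5) or an SAE report, which Protocol 7.5 requires within 24 hours of awareness whatever the visit schedule, could count as follow-up data. Many non-returning patients would then stay in. This stands: the understatement is conditional on the narrower reading and on such patients existing.

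**Dropout before Month 18 is not evidence of loss before the first follow-up.** A reader might take the dropout noted in SAP 1.10 as showing that many patients are excluded. Patients who left after Month 3, 6 or 12 have follow-up data, and their reasons are tabulated. The documents do not say how many left earlier.

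**Identical ITT and Safety Sets are not in themselves an error.** A reader might see a contradiction between SAP 1.10 and SAP 1.8. SAP 1.10 says only that a safety set was defined, not that it differs from the ITT Set, and in a single-arm study the two may coincide.

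**Requiring some follow-up for event percentages is defensible.** A treated patient never seen again has unknown event status, and including that patient counts them as event-free. A reader might infer that the adverse event rates are biased in a known direction. The documents do not support this, since the direction depends on whether the excluded patients had events. This argument covers denominators, however. It does not justify dropping a reported event, and it does not apply to the termination table, where not returning is the outcome itself.

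**Little rests on these tables.** They are descriptive, and the protocol planned no safety analysis. This limits the importance of the point without removing the selection.

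**Conclusion.** The point holds for the course-of-study tables. SAP 1.8 makes follow-up data a condition for entering the table that counts loss to follow-up, and nothing else in the plan reveals how many treated patients are left out. If the condition means a post-baseline visit and the excluded were mostly lost to follow-up, early loss is understated. Mean duration is overstated if their durations were shorter.

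The size cannot be determined from the documents and may be nil. Under the assumed counts above, a 20.0% loss would be shown as 17.9% down to 5.9% for 5 to 30 excluded patients.

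For adverse events the effect on percentages is small and of no fixed direction. The sounder reason for change there is that a reported event could be dropped. The change in TWPI is analysed on the Per Protocol Set and does not depend on the Safety Set definition.

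**What to change.** 1. **SAP 4:** base the termination and study duration tables on all enrolled patients, and treatment duration on all patients with at least one dose. Because SAP 1.9 dates enrolment from consent, the enrolled group may include patients never dosed; show them on a separate line.
2. **SAP 2.1:** add the numbers enrolled, treated, and treated without follow-up data, overall and by indication, and state what counts as follow-up data.
3. **SAP 1.8:** define the Safety Set as all enrolled patients with at least one dose, so that no reported event in a treated patient is left out. Footnote the event tables with the number who had no follow-up.

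This needs no new data, only edited definitions, a few added counts and one further population in the table programs. The cost in interpretation is small: patients with unobserved event status count as event-free in the event percentages, which the footnote lets the reader allow for.

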1. METHODOLOGY

The purpose of this statistical analysis plan is to provide detailed information on the statistical analysis of the data of study P13-990. The plan is based on the final protocol, incorporating administrative change 1, dated 17 December 2015.

1.1 *Introduction*

Ankylosing spondylitis (AS) and psoriatic arthritis (PsA) are both associated with often debilitating clinical symptoms, reduced functional impairment and significant impact on quality of life. As a consequence both diseases imply a significant economic burden, arising from both the direct costs of medical and disability. Health economics data becomes increasingly important to justify the costs of medicines.

Very limited data are available about the employment status and the work productivity of patients with AS and PsA in Belgium. The same is true for the impact of adalimumab treatment on employment status and work productivity.

The aim of this study is to analyse the employment status and work productivity of patients with AS and PsA before and after the start of adalimumab and to look at the relationship between employment status, work productivity, disease activity and clinical evaluations.

1.2 *Study Objectives and Endpoints*

1.2.1 *Study Objectives*

The main objective of the study is to observe in daily practice the evolution of work productivity over 18 months in AS and PsA patients after the start of adalimumab treatment.

The following questions were addressed:

- What is the employment status of AS and PsA patients with active disease before initiation of adalimumab?
- In the patients who work at baseline, what is their work productivity?
- Does adalimumab therapy enable people with AS and PsA to return to work or work more productively?

The secondary objectives are to:

- Investigate if there is a difference in evolution of employment status and work productivity after initiation of adalimumab treatment between AS and PsA patients throughout the study
- Investigate the relationship between disease activity and employment situation and the relationship between clinical evaluations and employment situation at baseline and after 18 months
- Investigate possible correlations between disease activity and work productivity and between clinical evaluations and work productivity

1.2.2 *Study Endpoints*

The primary endpoints is Total Work Productivity Impairment (TWPI) due to AS/PsA:

18 months versus baseline in all patients, measured by the WPAI-SHP questionnaire.

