3. ONSET DATA

The analysis is performed for all patients and broken down by indication.

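### The two baseline questions of the primary objective are described in the Per Protocol Set, a group selected partly on what happened after baseline

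*SAP*

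**What the plan says.** SAP 1.2.1 lists three questions under the primary objective. The first two are cross-sectional: "What is the employment status of AS and PsA patients with active disease before initiation of adalimumab" and "In the patients who work at baseline, what is their work productivity".

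SAP 1.8 then fixes the populations:

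- Baseline and efficacy: "All baseline and efficacy data will be analysed on the basis of the PPS".
- The PPS is defined as "All patients of the ITT Set without any major protocol deviations". Deviations are graded minor or major at a data review before database lock; neither document says what counts as major.
- The ITT Set is made up of enrolled patients "who received at least one dose of adalimumab, and for whom any follow-up data are available". The Safety Set is defined in the same words.
- One exception brings in the ITT Set: "In case the difference between the ITT Set and PPS exceeds 10% of the patients of the PPS, the TWPI data will also be analysed".
- Safety output and the study-course tables use the Safety Set.

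Protocol 10.3.1 is the origin of the PPS-first approach. It also planned a TWPI analysis on the ITT set without any trigger, and it did not define that set by follow-up.

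**The concern.** Answering what share of patients worked before adalimumab, and how productive the workers were, takes an eligible patient and a baseline record. Nothing later is needed. Under SAP 1.8 a patient must also have come back at least once and have no major deviation, including one that arose during follow-up. A patient who meets every entry criterion, starts treatment, completes the employment form and the WPAI, and is never seen again does not appear in the baseline tables.

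If such patients differ from the rest in employment or productivity, the baseline description is shifted. Both documents say that very little is known about employment and productivity in these patients in Belgium, so the baseline picture is a main product of the study in its own right.

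**Working it through.** **Step 1. Which outputs are affected.** Baseline employment status is in SAP 3.3. WPAI question 1 and baseline absenteeism, presenteeism, TWPI and activity impairment are in SAP 5.1. Work status against clinical measures at baseline is in 5.10, and the baseline correlations are in 5.11. All are baseline or efficacy data, so all fall on the PPS.

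**Step 2. Whether another set fills the gap.**

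- SAP 2.2 covers all enrolled patients but reports only study dates.
- SAP 3 says "The analysis is performed for all patients and broken down by indication". The same sentence opens SAP 4, which uses the Safety Set, and SAP 1.7 also sets all patients against the AS and PsA subgroups. The natural meaning is AS and PsA pooled, not an all-enrolled population.
- SAP 4 reports changes in employment and lists the patients who changed. It gives no baseline distribution, and the Safety Set also requires follow-up.
- The conditional ITT analysis is limited to TWPI, so it never covers employment status.

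**Step 3. What the 10% trigger can see.** The rule is (ITT − PPS)/PPS > 10%. Patients without follow-up are in neither set, so they do not enter the rule. Take 200 enrolled (the planned number) and 40 outside the PPS (assumed):

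- All 40 have major deviations but some follow-up: ITT = 200, PPS = 160, 40/160 = 25%. The trigger fires.
- All 40 have no follow-up: ITT = 160, PPS = 160, 0/160 = 0%. It does not fire.

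With ITT = 200, up to 18 deviation exclusions also pass without an ITT analysis: 18/182 = 9.9%, while 19/181 = 10.5%.

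**Step 4. Size of a possible shift.** The plan has no figure for this point. Its only precision figures concern the TWPI change: 200 × 0.65 × 0.80 = 104, given as about 100 patients, and the printed intervals reproduce with a t quantile on 99 degrees of freedom (half-widths 4.72 for SD 23.8 and 5.95 for SD 30.0). They say nothing about who is missing at baseline.

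Let f be the fraction of eligible patients with baseline data who are outside the PPS, and d the employment rate inside minus the rate outside. Then

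shift = p_PPS − [(1 − f) × p_PPS + f × p_out] = f × d.

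Both f and d are assumptions:

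| f | d = 10 points | d = 20 points | d = 30 points | 95% half-width at 65% employed, n in PPS |
|---|---|---|---|---|
| 5% | 0.5 | 1.0 | 1.5 | 6.8 (n = 190) |
| 10% | 1.0 | 2.0 | 3.0 | 7.0 (n = 180) |
| 20% | 2.0 | 4.0 | 6.0 | 7.4 (n = 160) |
| 30% | 3.0 | 6.0 | 9.0 | 7.9 (n = 140) |

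The half-width is 1.96 × √(0.65 × 0.35/n). With all 200 patients it is 6.6, so the loss of precision is minor. A negative d reverses the sign of the shift. The same product applies to mean baseline TWPI, with f taken among workers and d the difference in mean TWPI; the documents supply neither.

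**The case against.** The strongest reply is that the selection may be slight. One follow-up record of any kind keeps a patient in the ITT Set, and Month 3 is only a preferred visit time, so a patient first seen again much later still counts. In an observational study with no added visits or procedures, major deviations after baseline may be rare. Some major deviations may be entry failures, which any sensible baseline set would also remove. The primary endpoint is the change in TWPI, and a single set gives baseline and change tables the same patients. All of this stands. It limits the likely size of the problem, but it does not supply a set that contains the patients without follow-up.

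Three stronger readings are tempting and should be resisted.

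- A reader might infer that both questions are answered exclusively in the PPS. For TWPI that is inexact: SAP 1.8 does not restrict the conditional ITT analysis to change scores, so baseline TWPI may also appear there. The follow-up condition remains.
- A reader might take the dropout before Month 18, which SAP 1.10 calls important, as the number excluded. It is not, because a patient who leaves after one follow-up record stays in the ITT Set.
- A reader might conclude that baseline employment is overstated. The documents give no direction.

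**Conclusion.** The point holds as a matter of population definition: two questions that need only baseline data are described in a group chosen partly on later events, and no planned table covers the eligible patients left out. That this distorts the result is possible, not shown. The range of 0.5 to 9 points rests entirely on the assumed f of 5% to 30% and d of 10 to 30 points. Within that grid, only the most extreme combination exceeds the sampling half-width. The change-from-baseline analysis of TWPI is not affected. The change is worth making because it is cheap and because it would replace these assumptions with observed numbers.

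**What to change.** In SAP 1.8, add a Baseline Set: all enrolled patients who met the eligibility criteria and have baseline data, regardless of follow-up or of deviations after baseline. Then:

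- use it for SAP 3, the baseline columns of 5.1, and the baseline parts of 5.10 and 5.11;
- keep the PPS for changes from baseline;
- tabulate baseline employment status and WPAI scores for patients inside and outside the PPS, with the number in each group;
- at the data review before lock, mark each major deviation as an entry failure or a later event, so that the set can be built;
- record the departure from protocol 10.3.1 in SAP 1.10.

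The cost is one population flag and some SAP wording; the data are already collected. The downside is that baseline and change tables will have different denominators, which must be labelled.

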10.3 Statistical Methods

10.3.1 Analysis Sets

The statistical analysis will primarily be based on the Per Protocol analysis set consisting of the patients without major protocol violations. The TWPI-SHP data will also be analyzed on the Intention to Treat set.

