10.3.2 Statistical Analysis

The study is essentially descriptive. The numerical variables will be analyzed applying descriptive statistics (mean, 95% confidence interval on the mean, standard deviation, minimum, 1st quartile, median, 3rd quartile, maximum, number of observations).

Quantitative variables will be described by means of frequencies and percentages for the

different categories. For the variables recorded for both AS and PsA patients the descriptions will be given for all patients as well as separately for each subgroup.

The analysis of the evolution of the work productivity data, the health-related quality of life scores, and the disease activity measures and clinical evaluations will be based upon data collected during time windows around the foreseen routine study visits.

The relationship between disease activity and work status and between clinical evaluations and work status will be evaluated by comparing the onset data for patients currently employed and patients not employed at the baseline visit, and by comparing the data from the 18 month time window for patients currently employed and patients not employed at the corresponding visit.

The relationship between disease activity and work productivity and between clinical evaluations and work productivity will be evaluated on the basis of the correlations with the TWPI for the baseline data.

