1.4 Sample Size Justification

The main objective of this study is to observe the working status in AS and PsA patients before and after the start of adalimumab therapy in daily practice. The primary variable is the change in total work productivity impairment (TWPI) due to AS/PsA between baseline and Month 18. The change will be evaluated in a descriptive way by means of the mean change observed in the study and its 95% confidence interval.

The number of patients to be enrolled (200) was determined on the basis of the recruiting capacity of the participating investigational sites during the foreseen recruitment period of 12 months.

Based on data from Reilly et al¹ it is estimated that about 65% of the patients of the study population are working and therefore evaluable for work productivity impairment.

Supposing that 80% of the employed patients have data available over an 18 month period, the mean change in TWPI will be estimated on the basis of data for about 100 patients.

Based on data for a 16 week treatment period it is estimated that the standard deviation of the change in TWPI will be about 23.8. Since the estimate to be made is for an 18 month treatment period, 95% confidence intervals are also calculated for a somewhat more important standard deviation, arbitrarily set equal to 30.0.

¹ Reilly MC, Zbrozek AS, Dukes EM. The validity and reproducibility of a work productivity and activity impairment instrument. *Pharmacoeconomics*. 1993; 4: 353–65.

The table below contains 95% confidence intervals on the mean change for some possible mean changes (-10.0, -15.0 and -20.0), and for standard deviations (SD) of 23.8 and 30.0, supposing data will be available for 100 patients:

Mean change	SD	95% CI
-10.0	23.8	[-14.7 ; -5.3]
-15.0	23.8	[-19.7 ; -10.3]
-20.0	23.8	[-24.7 ; -15.3]
-10.0	30.0	[-16.0 ; -4.0]
-15.0	30.0	[-21.0 ; -9.0]
-20.0	30.0	[-26.0 ; -14.0]

These intervals show that quite precise estimates can be obtained of the change in TWPI on the basis of the planned sample size.

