2. SAMPLE DESCRIPTION

2.1 Study Population

- Number of patients in the ITT Set and the PPS, and number of patients in the ITT Set and the PPS broken down by indication.

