5. EFFICACY DATA

5.1 WPAI Questionnaire

- Frequency distribution of professional activity at baseline, at each visit, and at the last observation.
- Frequency distribution of professional activity at each visit and at the last observation, broken down by professional activity at baseline.

For absenteeism, presenteeism, TWPI, and percentage activity impairment:

- Descriptive statistics at baseline, at each visit, and at the last observation.
- Descriptive statistics of the change between baseline and each visit, and between baseline and the last observation.

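### The SAP makes the protocol's unconditional ITT analysis of TWPI depend on a 10% head count that ignores who has a TWPI change

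*SAP*

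**What the plan says.** Protocol 10.3.1 bases the analysis primarily on the PPS and then adds: "The TWPI-SHP data will also be analyzed on the Intention to Treat set". It attaches no condition.

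SAP 1.8 states: "All baseline and efficacy data will be analysed on the basis of the PPS". It then allows the ITT analysis of TWPI only "In case the difference between the ITT Set and PPS exceeds 10% of the patients of the PPS". SAP 1.10 lists this among the changes from the protocol: "It was decided only to perform the latter analysis in case the difference between the two analysis sets exceeds 10" per cent of the PPS patients. No reason follows, although four of the five other changes in that section come with one.

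Under SAP 1.8, the ITT Set is every enrolled patient with at least one dose and any follow-up data, and the PPS is the ITT Set less patients with major deviations. Neither definition mentions employment or an available TWPI. The SAP's sample size section nevertheless expects that "about 65% of the patients of the study population are working and therefore evaluable for work productivity impairment", and that 80% of those will have data over 18 months.

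**The concern.** The ITT analysis is the protocol's only check on whether removing patients for protocol deviations changes the primary result. The SAP turns it into a conditional analysis, and the condition measures the wrong quantity. What matters for the mean change in TWPI is how many excluded patients have such a change and how far their changes differ from the rest. A head count over all patients captures neither, so it can fail both ways:

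- it can leave the check unrun when the exclusions fall among patients who carry the primary endpoint;
- it can call for the check when the exclusions fall among patients with no Month 18 change, in which case the two Month 18 results are identical.

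Nothing else in the SAP fills the gap. SAP 2.1 reports the "Number of patients in the ITT Set and the PPS", and the descriptive statistics include available and missing counts. Employment changes are described on the Safety Set. The last-observation analysis deals with dropout and stays within the PPS. None of these gives a TWPI estimate outside the PPS.

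**Working it through.** **Inputs**

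- Planned enrolment 200 (Protocol 6.2).
- 65% working, 80% of those with 18-month data, SD of the change 23.8 or 30.0, mean changes -10, -15 and -20 (Protocol 10.1, SAP 1.4).
- Trigger: ITT − PPS > 10% of PPS (SAP 1.8).
- Assumptions, because the documents give no figure: an ITT Set of 200, and D, the difference in mean change between excluded and retained patients.

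**Step 1. Reproduce the plan's figures.** Patients with a Month 18 change: 200 × 0.65 × 0.80 = 104, which the plan rounds to about 100; the other 96 have none. The half-width of the 95% interval is t(0.975, n−1) × SD / √n. At n = 100 this is 4.72 for SD 23.8 and 5.95 for SD 30.0, which reproduces all six tabulated intervals.

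**Step 2. Where the trigger lies.** With x exclusions from an ITT Set of N, the check is not run while x ≤ 0.10 × (N − x), that is x ≤ N/11. For N = 200, N/11 = 18.2:

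- 18 exclusions: 18/182 = 9.9%, not run.
- 19 exclusions: 19/181 = 10.5%, run.

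**Step 3. What 18 unchecked exclusions could do.** If e of the n evaluable patients are excluded, the ITT and PPS means differ by (e/n) × D. Suppose the excluded patients show no change and the others change by -15, so that D = 15.

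| How the 18 fall | Evaluable patients excluded | Shift in mean (points) |
|---|---|---|
| Even spread | 18 × 104/200 = 9.36 (9.0%) | 0.09 × 15 = 1.35 |
| Random, 2.5% point | 5 | 5/104 × 15 = 0.7 |
| Random, 97.5% point | 13 | 13/104 × 15 = 1.9 |
| All evaluable | 18 (17.3%) | 18/104 × 15 = 2.6 |

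The random rows are hypergeometric: 18 drawn from 200, of whom 104 are evaluable. The last row has a random chance of 3.6 × 10⁻⁶ and is a bound, not an expectation.

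**Step 4. Compare with the planned precision.**

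- Even spread, n = 100: 1.35/4.72 = 29% (SD 23.8); 1.35/5.95 = 23% (SD 30.0).
- Even spread, the 95 patients left (half-widths 4.85 and 6.11): 28% and 22%.
- All 18 evaluable, the 86 left (half-widths 5.10 and 6.43): 2.60/5.10 = 51% and 2.60/6.43 = 40%.

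**Step 5. Vary the assumptions.**

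- Even spread with D = 10 or 20, the plan's other mean changes: 0.9 or 1.8 points. With D = 5: 0.09 × 5 = 0.45 points, about 10% of 4.72.
- ITT Set of 180: up to 16 unchecked (16/164 = 9.76%), even-spread shift 16/180 × 15 = 1.33.
- ITT Set of 150: up to 13 unchecked (13/137 = 9.49%), shift 13/150 × 15 = 1.30.

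**Step 6. The opposite failure.** If 19 exclusions all come from the 96 patients without a Month 18 change, the trigger is met, yet the ITT and PPS results for that change are the same.

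**The case against.** The case for leaving the SAP as it stands has real substance.

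- **The change is declared.** SAP 1.10 states both the old and the new rule, and Protocol 10.0 leaves the detailed plan to a later document. This stands: it is a disclosed weakening, not a hidden contradiction.
- **The trigger limits discretion.** It is numerical, and deviations are classified before database lock, so the rule does not turn on how the ITT result looks. It also spares readers near-duplicate tables. This is fair, but it does not make a count of all patients a suitable measure for an endpoint that about half of them will have.
- **The contrast is assumed.** No text supports zero change in every excluded patient, or exclusions at exactly the largest unchecked number. That is right; with D = 5 or fewer exclusions the shift is small. But D cannot be known until the ITT analysis is run, which is why the protocol asked for it.
- **The opposite failure concerns Month 18 only.** By the planning figures 200 × 0.65 = 130 patients work at baseline, so 130 − 104 = 26 of the 96 could still contribute to baseline, earlier visits or the last observation. Of 19 exclusions spread over the 96, about 19 × 26/96 ≈ 5 would be such patients. An ITT run could therefore alter those tables, and the point is limited accordingly.
- **The consequence is limited.** Protocol 10.3.2 says "The study is essentially descriptive", and PPS primacy is the protocol's own choice. Both points bear on priority; neither supplies the missing estimate.

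**Conclusion.** The concern holds. The SAP replaces an unconditional check on the primary endpoint, without a stated reason, by one that depends on a count unrelated to who has a TWPI change. If the trigger is not met, readers will know how many patients were excluded but not whether this moved the primary estimate.

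The likely size is modest: about 1.35 points under the stated assumptions, with 0.7 to 1.9 if the 18 exclusions fall at random. It becomes larger only if exclusions concentrate in working patients, which nothing in the documents suggests. The actual set sizes are not given. SAP 1.10 reports that a substantial share of patients left before Month 18, so fewer than 104 may be evaluable, and each excluded evaluable patient would then weigh more. No error rate or power figure is affected. This is a change that should be made, but not one that undermines the study.

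**What to change.** Delete the 10% condition from SAP 1.8 and the matching paragraph of SAP 1.10. State that the TWPI tables of SAP 5.1, including "Descriptive statistics of the change between baseline and each visit, and between baseline and the last observation", will be reported on the ITT Set in all cases, beside the PPS, as the protocol provides.

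The cost is wording in two sections and a second run of the existing TWPI programs on a set already defined. No new data are needed. The downside is one more set of tables, which will be nearly identical to the PPS tables if few patients are excluded.
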